9.1 Declaration of Helsinki

The investigator will ensure that this study is conducted in full conformity with the 7th revision of the 1964 Declaration of Helsinki.

9.2 Good Clinical Practice

The study will be conducted in accordance with the guidelines laid down by the International Conference on Harmonisation for Good Clinical Practice (ICH GCP E6 guidelines).

9.3 Independent Ethics Committee Approval

(i) Initial Approval

Prior to the shipment of the medical device and accessories and the enrolment of subjects, the REC must provide written approval of the conduct of the study at named sites, the protocol and any amendments, the Subject Information Sheet and Consent Form, any other written information that will be provided to the subjects, any advertisements that will be used and details of any subject compensation. HRA approval is also needed before study start at each participating site.

(ii) Approval of Amendments

Proposed amendments to the protocol and aforementioned documents must be submitted to the REC for approval as instructed by the Sponsor. Amendments requiring REC approval may be implemented only after a copy of the REC's approval letter has been obtained.

Amendments that are intended to eliminate an apparent immediate hazard to subjects may be implemented prior to receiving Sponsor or REC approval. However, in this case, approval must be obtained as soon as possible after implementation.

HRA approval is also needed for implementation of amendments at respective participating sites.

(iii) Annual Progress Reports

The Sponsor and REC will be sent annual progress reports in accordance with national requirements.

(iv) End of Trial Notification

The Sponsor and REC will be informed about the end of the trial, within the required timelines.

9.4 Sponsorship, Insurance and Indemnity

Imperial College London will act as the main Sponsor for this study. Delegated responsibilities will be assigned to the NHS trusts taking part in this study. Imperial College London holds negligent harm and non-negligent harm insurance policies which apply to this study.

9.5 Trial Registration

The study will be registered on a trial database in accordance with requirements of the International Committee of Medical Journal Editors (ICMJE) regulations. The trial will be registered on clinicaltrials.gov.

9.6 Informed Consent

Only patients with capacity to consent will be considered eligible for recruitment. Subjects should be provided with a copy of the signed Subject Information Sheet/Informed Consent Form document. The original Informed Consent Form should be retained with the source documents. Should a patient lose the capacity to consent during the trial follow-up period, the participant would be withdrawn from the study. Identifiable data or blood sample already collected with consent would be retained and used in the study. No further data or sample would be collected or any other research procedures carried out on or in relation to the participant.

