6.6 Permanent Discontinuation of Study Treatment and Withdrawal from Study

(i) Permanent discontinuation of study treatment

Subjects may discontinue study treatment for the following reasons:

- At the request of the subject.
- Adverse event/ Serious Adverse Event
- If the investigator considers that a subject's health will be compromised due to adverse events or concomitant illness that develop after entering the study.

(ii) Withdrawal from Study

Withdrawal from the study refers to discontinuation of study treatment and study procedures and can occur for the following reasons:

- Subject decision
- Loss to follow-up

(iii) Procedures for Withdrawal from Study

If a patient wishes to withdraw from the study, they will be asked at what level they wish to withdraw i.e. if they would like to terminate pacing treatment but are willing to attend followup visits, or if they do not wish to be contacted about the study including results of the study. Reason for and level of withdrawal must be recorded in the eCRF and medical records. Patients will not be replaced and follow-up should continue if the patient agrees. In the event that a subject wishes to terminate treatment after implantation of the study device, the patient's GP or direct medical care team will be notified and the patient will return to routine clinical care.

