7.3 Serious Adverse Events (SAE)

i) Definition of SAE

An SAE is defined as any event that

- Results in death;
- Is life-threatening*;
- Requires hospitalisation or prolongation of existing inpatient's hospitalisation**;
- Results in persistent or significant disability or incapacity;
- Is a congenital abnormality or birth defect;

* "Life-threatening" in the definition of "serious" refers to an event in which the subject was at risk of death at the time of the event; it does not refer to an event which hypothetically might have caused death if it were more severe.

** "Hospitalisation" means any unexpected admission to a hospital department. It does not usually apply to scheduled admissions that were planned before study inclusion or visits to casualty (without admission).

Medical judgement should be exercised in deciding whether an adverse event/reaction is serious in other situations. Important adverse events/reactions that are not immediately life-threatening, or do not result in death or hospitalisation but may jeopardise a subject, or may require intervention to prevent one of the other outcomes listed in the definition above should also be considered serious.

(ii) Reporting of SAEs

All SAEs will be reported to the Sponsor within 24 hours of an Investigator becoming aware of the event. Reporting procedures are detailed in the study's SAE reporting instructions. If the investigator becomes aware of safety information that appears to be related to the

medical device or study procedures, involving a subject who participated in the study, even after an individual subject has completed the study, this should be reported to the Sponsor.

All SAEs will be reviewed by the Chief Investigator or a designated medically qualified representative to confirm expectedness and causality.

Expected AEs in this population of patients with Heart Failure will include hospitalisations related to arrhythmia, worsening shortness of breath and chest pain.

Reporting of SAEs and review by the CI will be via the trial data collection system (InForm).

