8.2 Data Analysis

Patient characteristics will be summarized. Summaries of continuous variables will be presented as means and standard deviations if normally distributed, and as medians and inter-quartile ranges for skewed data, whilst categorical variables will be presented as frequencies and percentages.

The analysis will be performed according to the intention to treat principle.

(i) Endpoint Analysis

The primary outcome will be analysed using a two-level hierarchal model. We will include treatment, period and sequence effect within the model. Random subject effects will also be included in the regression model if appropriate. Differences in secondary outcomes will also be analysed using aforementioned two level hierarchal model. Normality will be checked and appropriate transformation or non-parametric methods will be used if it is not met.

All statistical tests will be two-tailed with a 5% significance level.

A separate statistical analysis plan will be prepared and finalised prior to database lock.

(ii) Safety Analysis

Safety analysis will consist of descriptive statistics of fluoroscopy time at the time of device insertion, pacing thresholds, R wave amplitude, lead impedance, the frequency of lead malfunction, hospitalisations and death. This will be reviewed by the Data Monitoring Committee.

(iii) Economic evaluation

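### Section 9.6 stops all data on a participant who loses capacity and makes no safety exception, which conflicts with the reporting duties in Sections 7.3 and 7.4

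*Protocol*

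**What the plan says.** Section 9.6 of the protocol (Informed Consent) sets three rules.

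- Withdrawal: "Should a patient lose the capacity to consent during the trial follow-up period, the participant would be withdrawn from the study".
- Data already held: "Identifiable data or blood sample already collected with consent would be retained and used in the study".
- Data from then on: "No further data or sample would be collected or any other research procedures carried out on or in relation to the participant".

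None of them mentions adverse events, device effects or vital status.

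The safety sections are written without any exemption for such patients. Section 7.3(ii) states: "All SAEs will be reported to the Sponsor within 24 hours of an Investigator becoming aware of the event". It names InForm as the route, which Section 10.3 identifies as the study's electronic data capture system. For safety information that appears related to the device or the study procedures, in anyone who took part, 7.3(ii) goes further: "even after an individual subject has completed the study, this should be reported to the Sponsor". Section 7.4 sends device incidents to the manufacturer within 48 hours and has the sponsor informed of all serious adverse device effects. Section 7.5 sends related, unexpected SAEs to the ethics committee within 15 days.

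Section 8.2(ii) lists the safety outcomes, which include "lead impedance, the frequency of lead malfunction, hospitalisations and death". Section 6.6(ii) names subject decision and loss to follow-up as reasons for withdrawal, and does not mention loss of capacity.

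**The concern.** A patient who loses capacity in this trial still carries the implanted system. That patient can still be admitted, die, or have a lead or device problem, and the local team will usually know. Sections 7.3 and 7.4 tell the investigator to report this, and Section 9.6 tells the investigator to collect nothing more. Two sites could resolve the conflict in opposite ways, and both could cite the protocol.

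The gap does not fall at random among patients. Section 7.3(i) makes persistent or significant disability or incapacity a criterion of seriousness, so an adverse event that causes lasting loss of capacity is itself an SAE. Section 9.6 would close the record just after such an event, before its outcome is known. What is at stake is complete counts of hospitalisations, deaths and device events, both in the final safety analysis and in the event rates that Section 1.3 relies on the Data Monitoring Committee to review.

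**Working it through.** **The passages side by side, for a participant who has lost capacity**

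| Question | Section 9.6 | Sections 7.3 to 7.5 |
|---|---|---|
| May new information on this person enter the trial record? | No; the bar covers anything in relation to the participant | Yes; all SAEs, within 24 hours, through InForm |
| Does the duty end when the person leaves the trial? | Collection ends at loss of capacity | Related safety information is still due after completion |
| Are device effects exempt? | No exemption stated | All serious adverse device effects go to the sponsor; incidents go to the manufacturer |

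1. An SAE report is entered in InForm, the trial's data capture system. Filing one is therefore collecting data in relation to the participant.
2. Section 9.6 forbids that without exception, and Section 7.3(ii) requires it without exception. Read literally, both cannot be followed.
3. Data already collected are kept. What is at risk is what comes later: the outcome of the incapacitating event, and subsequent deaths, hospitalisations and device events.
4. These are outcomes named in Section 8.2(ii), so the loss reaches a stated analysis.

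**Does it matter for the primary endpoint?**

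Inputs from Section 8.1: difference 0.7, SD of the paired difference 2.4, two-sided alpha 0.05, power 90%, 126 evaluable, 21% combined mortality and dropout, 160 in total.

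The plan's own figures reproduce.

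- Normal approximation: n = ((1.960 + 1.282) × 2.4/0.7)² = 123.5, so 124.
- Paired t-test: power is taken from the noncentral t distribution with n − 1 degrees of freedom and noncentrality (0.7/2.4)√n. At n = 125 it is 89.9% and at n = 126 it is 90.1%, so 126 is the smallest adequate number.
- Inflation: 126/0.79 = 159.5, so 160.

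The protocol gives no rate of capacity loss. There are two cases.

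- Such withdrawals fall within the 21%: 160 × 0.79 = 126.4, so 126 remain evaluable and power stays at 90.1%.
- They come on top of the 21% (the percentages are assumptions, shown as a range only):

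| Extra loss | Evaluable | Power |
|---|---|---|
| 1 point | 160 × 0.78 = 124.8, so 124 | 89.7% |
| 2 points | 160 × 0.77 = 123.2, so 123 | 89.4% |
| 5 points | 160 × 0.74 = 118.4, so 118 | 88.1% |

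Even at 5 extra points the fall is 2.0 percentage points. The point therefore rests on the safety record and not on power.

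**The case against.** The best defence is that the sections can be read together. Section 9.6 sits under informed consent and can be taken to stop research collection, while 7.3(ii) describes what an investigator does on becoming aware of an event, which is passive vigilance. The clause on reporting after completion concerns completers and only device- or procedure-related information. Separate SAE reporting instructions exist and are not part of this document. Stopping on loss of capacity is also a matter for the sponsor and the ethics committee, and is not wrong in itself.

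Much of this stands. The softer reading is plausible and may be what was meant. But 9.6 does not say it, and its wording reaches anything in relation to the participant. The general duty to report all SAEs is not limited to completers or to related events, so the conflict does not depend on the narrower clause.

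A reader might also infer stronger points that the protocol does not support.

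- **That Section 6.6 contradicts 9.6.** Section 6.6(ii) gives a list that 9.6 extends. The list is incomplete, but it gives no opposite instruction. Section 6.6(iii) continues follow-up if the patient agrees, which a patient without capacity cannot do.
- **That every patient who is briefly sedated or delirious is withdrawn.** Section 9.6 sets no duration and has no recovery clause. That is an ambiguity to settle, not a stated rule for temporary loss.
- **That the peak VO₂ comparison is biased because the illness depends on the pacing state.** Nothing in the protocol supports that dependence. Many patients with lasting incapacity could not complete an exercise test under any rule.

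**Conclusion.** The concern holds as a conflict of instructions with a consequence for safety data. Section 9.6 imposes a blanket data stop that cannot be squared literally with 7.3(ii) and 7.4. If it is followed, later outcomes and events in implanted patients are left out of the analysis in 8.2(ii).

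The number of patients is unknown because no rate is given, and it is probably small. The safety analysis is descriptive, and the initial report of the incapacitating event may well be on file. Power is unchanged if these losses lie within the 21% allowance, which is the natural reading of a combined mortality and dropout figure. Otherwise it falls to between 89.7% and 88.1% over the assumed 1 to 5 extra points. It would be wrong to count the same patients both against the allowance and off the 126.

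The conclusion assumes that 9.6 is applied as written and that no document outside the protocol already makes the exception.

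**What to change.** - **Section 9.6, reconciled with 7.3 to 7.5:** state that on loss of capacity research visits, samples and procedures stop, but that SAEs, adverse device effects and deaths of which investigators become aware are still reported.
- **Consent form and information sheet:** word them so that entry consent covers this continued reporting. Those pages are not in the copy reviewed, so whether they already do so is not known.
- **Section 6.6(ii):** add loss of capacity to the reasons for withdrawal.
- **Sections 9.6 and 6.6:** have the sponsor state whether a participant who regains capacity may resume study assessments on reconfirmed consent.

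Section 6.6(ii) defines withdrawal as ending study treatment as well as study procedures. The sponsor should therefore settle that link itself; no rule on stopping or continuing pacing is proposed here.

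The cost is a wording amendment that needs ethics approval. It adds no visits and no patients.

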9.7 Contact with General Practitioner

It is the investigator's responsibility to inform the subject's General Practitioner by letter that the subject is taking part in the study provided the subject agrees to this, and information to this effect is included in the Subject Information Sheet and Informed Consent. A master letter template will be kept in the Investigator Site File. A copy of the letter sent to each participant's GP should be filed in the patient's medical notes.

9.8 Subject Confidentiality

The investigator must ensure that the subject's confidentiality is maintained. On the CRF or other documents submitted to the Sponsor, subjects will be identified by a subject ID number only. Documents that are not submitted to the Sponsor (e.g., signed informed consent form) should be kept in a strictly confidential file by the investigator.

To facilitate follow-up visits of patients recruited at hospitals other than the Hammersmith Hospital, patients will be registered with the Hammersmith. Patient contact details and GP details will be made available to study's research team at Imperial College London. The research team will have access to data on InForm collected at earlier study visits. Patient medical records will be requested only if deemed necessary.

The investigator shall permit direct access to subjects' records and source document for the purposes of monitoring, auditing, or inspection by the Sponsor, authorised representatives of the Sponsor, Regulatory Authorities and RECs.

Principles of Data Protection Act 1998 will be adhered to.

9.9 End of Trial

The end of the trial will be after the last subject last visit and once the study database is locked.

9.10 Study Documentation and Data Storage

The investigator must retain essential documents until notified by the Sponsor, and for at least ten years after study completion. Subject files and other source data (including copies of protocols, CRFs, original reports of test results, correspondence, records of informed consent, and other documents pertaining to the conduct of the study) must be retained. Documents should be stored in such a way that they can be accessed/data retrieved at a later date. Consideration should be given to security and environmental risks.

No study document will be destroyed without prior written agreement between the Sponsor and the investigator. Should the investigator wish to assign the study records to another party or move them to another location, a written agreement must be obtained from the Sponsor.

10 DATA MANAGEMENT

10.1 Source Data

Source documents will be specified for CRFs that required source data verification. Where data are directly entered into the eCRF it will also be documented.

10.2 Language

CRFs will be in English. Generic names for concomitant medications should be recorded in the CRF wherever possible. All written material to be used by subjects must use vocabulary that is clearly understood, and be in the language appropriate for the study site.

10.3 Database

The electronic data capture system InForm[™] will be used in this study. The database will have built-in validation checks and generate auto-queries. The Trial Monitor will raise manual queries as required.

10.4 Data Collection

Details of procedures for eCRF completion will be provided in a study manual.

11 STUDY MANAGEMENT STRUCTURE

11.1 Trial Steering Committee

A Trial Steering Committee (TSC) will be convened including an independent Chair, independent clinician, the Chief Investigator and Trial Manager. The role of the TSC is to provide overall supervision of trial conduct and progress.

11.2 Trial Management Group

A Trial Management Group (TMG) will be convened including the Chief Investigator, coinvestigators and key collaborators, trial statistician and trial manager. The TMG will be responsible for the day-to-day conduct of the trial and operational issues.

11.3 Data Monitoring Committee

A data monitoring committee composed of three independent professionals and including an independent statistician will be convened. The frequency of meeting and the data to be reviewed and whether the data will be blinded/unblinded will be documented in the DMC charter.

11.4 Early Discontinuation of the Study

The DMC will define the criteria for early discontinuation and make recommendations to the TSC as required.

11.5 Risk Assessment

A study-specific risk assessment will be performed prior to the start of the study to assign a risk category. The risk assessment will be carried out by the ICTU QA Manager in collaboration with the Study Manager and the result will be used to guide the monitoring plan. The risk assessment will consider all aspects of the study and will be updated as required during the course of the study.

11.6 Monitoring

The study will be monitored periodically by trial monitors to assess the progress of the study, verify adherence to the protocol, ICH GCP E6 guidelines and other national requirements and to review the completeness, accuracy and consistency of the data.

11.7 Quality Control and Quality Assurance

Quality Control will be performed according to ICTU internal procedures. The study may be audited by a Quality Assurance representative of the Sponsor and/or ICTU. All necessary data and documents will be made available for inspection.

11.8 Disclosure of Data and Publication

Information concerning the study, patent applications, processes, scientific data or other pertinent information is confidential and remains the property of the Sponsor. The investigator may use this information for the purposes of the study and related studies in the future.

All information obtained as a result of the study will be regarded as CONFIDENTIAL, at least until appropriate analysis and review by the investigator(s) are completed.

Anonymised study data will be shared with the other research institutions as well as private sector companies within and outside of the European Union, where data protection laws may not be the same. These data will be used for non-commercial research purposes. All reasonable steps will be taken to protect your privacy.

Appendix 2. Summary of study procedures/assessments by visit

‡ Visit at local hospital where patient was identified

^ Performed at Imperial College Healthcare NHS Trust

& Taken at screening visit or within the past 18 months

* RUM questionnaire only at visit 1, all questionnaires for visits 3-5

Either at local hospital or at Imperial College Healthcare NHS Trust £ Taken on the day or within the last 12 months

\$ Taken on the day of implantation or within the past 30 days

+ Taken at screening visit or within the past 18 months for patients with EF 36-40%

	Screening [*]	Implantation [#]	Randomisation [^]	Cross-over^	End of Study [^]
Visit	1	2	3	4	5
Month/Week/Day	- 2 to 6 months	-2 months (± 14 days)	0	6 months (± 14 days)	12 months (± 14 days)
Informed consent	Х				
Inclusion & exclusion criteria	Х				
Demography	Х				
Medical history	Х				
Vital signs	Х	Х	Х	Х	Х
Concomitant medication	Х				
Pregnancy test for women of child bearing age	Х				
Safety blood tests (Creatinine, Haemoglobin, PT, G+S)		X£			
ECG	X&	X\$			
Device Implantation		Х			
Post implantation chest radiograph		Х			
Pacing check			Х	Х	Х
Device programmed on/off			Х	Х	Х
CPET			Х	Х	Х
Echocardiography	X&		Х	Х	Х
BNP	X+		Х	Х	Х
QOL and Cost Effectiveness questionnaires (EQ5D-5L/MLHFQ and the HOPE-HF RUM)	X*		х	Х	Х
Haemodynamic optimisation			Х	Х	
Revelation of treatment sequence to patient					Х
His pacing on/off according to patient's choice (Patient can make decision later)					Х

Confidential
